Objective: This study aims to assess the levels of lens spoilage under standard wear and disinfection practices in order to determine the optimal lens replacement frequency of OK lens. Furthermore, this study will evaluate the health of anterior surface of the eye and lens comfort levels during one-year overnight use of OK lenses.

Study design: The proposed study uses a prospective, observational quasi-experimental research design where the contact lens spoilage from same participants will be observed over the time before and after contact lens wear. Individuals (between 18 to 40 years of age) with a refractive error between -1.00 and -4.00D of sphere and astigmatism ≤ 2.50 D will be recruited in the study. The eligible participants will receive study OK lenses during the dispensing visit, following the screening visit. Participants will attend total eight visits, including a follow up visit 2 weeks after the lens cessation.

Planned sample size: We are planning a study with an ordinal data response variable from matched pairs of study participants. We estimate that the difference in the lens spoilage grading between matched pairs is normally distributed with a standard deviation 0.9. To detect a true mean difference of 1.90 between pairs, we will need 12 subjects to achieve 80% power, assuming a Type I error rate of 0.05. To account for a 20% dropout rate, a total of 16 participants will be recruited.

Study procedure: All 16 participants participant will receive suitable OK lenses following the teaching of insertion and removal lens methods and lens care regimen. Participants will be

reviewed at regular visits (*Screening visit, baseline visit, 1 day, 7 days, 21 days, 6 months, 12 months and 2weeks lens cessation visit*). At each visit, the anterior surface of the eye will be assessed using clinical microscope and lens comfort levels will be assessed using Ocular Surface Disease Index questionnaire (OSDI) and Contact Lens Dry Eye Questionnaire-8 (CLDEQ-8). A photographic method will be used to qualitatively assess lens spoilage at each visit. Additionally, during the lens dispensing visit, the 6-month visit, and the 1-year visit, lens deposition will be quantitatively evaluated using established standard laboratory procedures.

Primary outcome: OK lens spoilage grading scores.

Secondary outcomes: Contact lens comfort Scores (OSDI, CLDEQ-8) and ocular surface changes.

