ii. **Qualitative assessment (On-eye):** After the lenses are worn by the participant, slit-lamp photographs will be captured to assess the lens surface quality (surface scratches and deposition) using the Zeiss SL 120 equipped with Cam Compact (Carl Zeiss Meditec AG, Jena).

iii. **Wettability assessment (On-eye):**

On-lens tear break-up time: In this test, participants will be asked to blink twice and hold the blink. Time from the last blink to the first random appearance of dry patch will be measured in seconds.

Fastness of dryness: The examiner will assess the fastness from the random appearance of dry patch to expand to the rest of the lens surface. Subjective grading – slow, medium and fast.

Grading of lens surface deposits and scratches:

- Surface deposits on the contact lens will be graded on a scale of 0 (absent, no deposits) to 4 (severe, deposits covering >75% of surface).
- Surface scratches
 - Extent: Front surface scratches (on eye) on the contact lens will be graded on a scale of 0 (absent, no scratches) to 4 (extensive, scratches covering >75% of surface).
 - Magnitude: Front surface scratches (on eye) on the contact lens were graded on a scale of 0 (absent, no scratches) to 4 (severe, very deep).

Contact lens comfort: Assessed by using Ocular Surface Disease Index (OSDI), the Contact Lens Dry Eye Questionnaire-8 (CLDEQ-8). The data obtained from this visit will serve as a baseline measurement.

After the lens surface assessment, participants will be trained on safe insertion and removal of OK lenses by the investigator. Once proficient, lens care procedures, including disinfection and storage, will be explained. Participants will be provided with contact lens care solutions. The details of contact lens care solutions are presented in **Table 2**. Participants will receive handouts detailing insertion, removal, and cleaning

instructions, along with an "**O-K Wear Time Journal**" to log lens use, bedtime, and wake times. Participants will be instructed to wear the lenses overnight for at least 6 hours. For after-hours support, contact details for the NSW Health Emergency Department will be provided in case of any unusual symptoms or issues.

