Since it takes approximately one week for vision to be optimal with the study OK lens wear, daily disposable soft contact lenses will be provided to participants, if participants are expected to drive to the research facility in all the follow-up visits. These soft contact lenses will correct any expected residual power. In this case, participants will be taught the insertion and removal and hygiene practices required for safe soft contact lens use by the investigators.

Table 2. The details of contact lens care solutions

Solutions	Disinfection system	Active ingredients
Menicare Plus	Multipurpose solution	Polyhexamethylene biguanide 0.0005%, Poloxamer 0.5%, Hypromellose 0.275%
Menicon Progent	Weekly protein remover, disinfectant and intensive cleaner	Liquid A: Sodium Hypochlorite 20.3mg, Liquid B: Potassium Bromide (KBr) 30.75mg

3. Follow-up visits (1-day overnight visit; 7-days visit; 14-days visit ;1month; 6 months; 9 months ;12 month; 2-weeks lens cessation visit): During each visit, visual acuity assessment, auto-refraction, subjective refraction, anterior eye health check and corneal topography will be repeated as outlined in the screening visit section. Contact lens comfort using questionnaires and qualitative assessment of lens spoilage will also be performed in each lens wear visit. Similarly, lens fitting assessment will be conducted using slit-lamp bio microscopy and fluoresceine except during the 2-weeks lens cessation visit. The **2-weeks lens cessation visit**, which occur approximately two weeks after the 12-month visit, during which participants will cease lens wear for two weeks. This cessation period allows for the evaluation of recovery and stabilization of eye surface parameters, providing baseline comparisons. It will also help detect any eye-related events requiring further evaluation.

All visits will be scheduled for a duration of approximately 1 hour (45-60 min) in the morning within 2 hours after waking and at these visits, lens care regimen and hygiene will be emphasised, and "OK Wear Time Journal" will be reviewed.

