Potential participants will be provided with Participant Information Sheets and Consent form (PISCF) to read, outlining the potential risks and benefits. There will be an opportunity to clarify details regarding the research study before participating. Interested participants, who contacted the investigators will be provided with PISCF through emails. All participants will be above the age of 18 years and will have adequate English language to be able to sign their consent for the study. The informed consent information sheet is attached.

Participants will be given at least 24 hours to review the PISCF before the screening visit. If they have any questions, they can contact the researchers. Written consent will be obtained at the screening visit, where participants will return the signed PISCF to the investigators. Only after consent is provided will the screening visit proceed.

Enrolment Procedure

The participant will only be considered enrolled into the study after the informed consent process has been completed and the participant has met all inclusion criteria and none of the exclusion ones. The participant will receive a study enrolment number, and this will be documented on all study documents.

V. STUDY OUTLINE

Table 3. Study outline and visit details.

Procedures/ Data (Y/N)	Screening visit (60 min)	Baseline visit (45-60 min)	1-day visit (45-60 min)	7-days visit (45-60 min)	21-days visit (45-60 min)	6-months visit (45-60 min)	12-month visit (45-60 min)	2-wk lens cessation visit (45-60 min)
Visit Window	N/A	N/A	N/A	± 2 days	± 2 days	± 7 days	± 7 days	± 2 days
Informed Consent	Y	N	N	N	N	N	N	N
Meet Inclusion / Exclusion Criteria	Y	N	N	N	N	N	N	N
Questionnaires	N	Y	Y	Y	Y	Y	Y	Y
Visual Acuity	Y	Y	Y	Y	Y	Y	Y	Y
Refraction	Y	Y	Y	Y	Y	Y	Y	Y
Anterior Eye Health Check	Y	Y	Y	Y	Y	Y	Y	Y

Procedures/ Data (Y/N)	Screening visit (60 min)	Baseline visit (45-60 min)	1-day visit (45-60 min)	7-days visit (45-60 min)	21-days visit (45-60 min)	6-months visit (45-60 min)	12-month visit (45-60 min)	2-wk lens cessation visit (45-60 min)
Visit Window	N/A	N/A	N/A	± 2 days	± 2 days	± 7 days	± 7 days	± 2 days
Corneal Topography	Y	Y	Y	Y	Y	Y	Y	Y
OK Lens Parameter Selection	N	Y	N	N	N	N	N	N
Lens Fitting Assessment	N/A	Y	Y	Y	Y	Y	Y	N
Lens Spoilage Assessment (qualitative)	N/A	Y	Y	Y	Y	Y	Y	N
Lens Spoilage Assessment (quantitative – protein assay)	N/A	Y	N	N	N	Y	Y	N
Lens compliance using “O-K Wear Time Journal”	N/A	Y	Y	Y	Y	Y	Y	Y

VI. SAFETY

1. Study Procedure Risks:

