The study hypothesises that OK lens spoilage, including scratches and surface deposits, as well as eye discomfort levels, will progressively worsen across the visits at baseline visit, 6 months and 12 months visit. All the statistical methods will be aimed to address the given hypothesis.

Once all data are collected, different tests will be conducted to establish whether they follow normal distributions. This step will ensure us to choose the appropriate statistical test based on the data distribution. Continuous variables will be expressed as means \pm standard deviations, while categorical variable will be reported as medians and interquartile ranges (IQR). The time

effect (baseline, 6month and 12 month) and between-group differences in lens deposition levels, lens wettability scores, eye discomfort data from questionnaires, and eye surface changes will be tested with repeated measures ANOVAs (post-hoc tests) or Friedman test, with Bonferroni correction, where appropriate. This method will assess whether there are significant differences in spoilage across the three time points. If significant, post-hoc tests will help confirm if the worsening follows a progressive pattern from baseline visit to 12 months.

This study will use Spearman's correlation test to evaluate the correlations between the questionnaires scores (eye discomfort levels) and clinical test results (deposition and scratches). This correlation analysis will determine how these subjective and objective measures relate, further supporting the study hypothesis if a correlation is found. A value of $P < 0.05$ will be considered as significant. Furthermore, we determine to explore the association between OK lens replacement schedules and keratitis risk. By tracking lens spoilage, patient symptoms, and clinical indicators of infection over 12 months, we intend to gather preliminary data on infection risk. Given the difficulty of detecting keratitis with a small sample, we will use lens spoilage indicators as proxies for risk. We will also track all eye-related adverse events. While we may not establish a definitive keratitis rate, our approach will generate valuable insights on factors affecting OK lens-related health and guide future research on optimal replacement schedules to reduce keratitis risk.

VIII. STORAGE AND ARCHIVING OF STUDY DOCUMENTS.

Data format and storage location

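### Spoilage is analysed by nominal visit only, although nights per week are not fixed and a wear journal is kept; lenses with different cumulative wear may be pooled as the same age

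*Protocol*

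**What the plan says.** The Summary gives the purpose of the spoilage data: they are collected "in order to determine the optimal lens replacement frequency of OK lens". The Rationale (section I) describes the two later assessments by duration of wear, at six months and one year.

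The wear instruction is in Detailed Study procedure, item 2 (Baseline visit): "Participants will be instructed to wear the lenses overnight for at least 6 hours". No number of nights per week is given. The same item issues a journal "to log lens use, bedtime, and wake times". Item 3 has the journal reviewed at visits, and Table 3 lists it in a row that begins "Lens compliance using". No other use is stated.

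Item 4 replaces the right lens at the 6-month visit, because the lens worn until then goes to the laboratory. Table 3 continues qualitative spoilage grading at 12 months and does not restrict it to one eye.

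Section VII, Statistical Analysis, tests the time "effect (baseline, 6month and 12 month) and between-group differences in lens deposition levels" by repeated measures ANOVA or Friedman test. It says of this approach: "This method will assess whether there are significant differences in spoilage across the three time points". The other named analysis is a correlation: "This study will use Spearman's correlation test to evaluate the correlations between the questionnaires scores (eye discomfort levels) and clinical test results". Neither uses nights or hours worn.

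**The concern.** A replacement interval depends on how spoilage builds up on a lens. If it builds up with use, visit month stands in for use, and it does so well only when participants wear their lenses about equally often and each graded lens has been in use since dispensing. The protocol does not fix the first condition. Its own replacement of the right lens breaks the second.

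At stake is what a 12-month result means. If some participants wear their lenses less often, the average 12-month grade describes a mixture of wear histories and may understate spoilage in a lens worn every night. A reader could not tell, because no summary of wear is planned beside the grades, even though the data for one will be collected.

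**Working it through.** The protocol gives no expected nights per week or adherence figure, so there is no planned number to reproduce. The checks below show what the documents fix and how much could depend on what they leave open.

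**1. Lens age at 12 months, by design.** Input: right lens replaced at 6 months (Detailed Study procedure, item 4). At the 12-month visit the left lens is about 12 months old and the right about 12 − 6 = 6 months old. With wear every night, that is 7 × 52 = 364 nights on the left and 7 × 26 = 182 on the right, a ratio of 2. No assumption about uneven adherence is needed. The 12-month laboratory assay is done on the left lens, so this affects the qualitative grading of the right lens, not the assay.

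**2. Cumulative nights under assumed use.** Nights = nights per week × weeks. The nights per week are assumptions.

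| Assumed nights per week | 6 months (26 weeks) | 12 months (52 weeks) | 12-month wear in months of nightly use (12 × k/7) |
|---|---|---|---|
| 7 | 182 | 364 | 12.0 |
| 5 | 130 | 260 | 8.6 |
| 4 | 104 | 208 | 6.9 |
| 3 | 78 | 156 | 5.1 |

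Between 7 and 5 nights a week the ratio is 364/260 = 1.4.

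**3. Visit windows are not the problem.** Table 3 allows ±7 days at both later visits. That is 7/182.5 = 3.8% of lens age at 6 months and 7/365 = 1.9% at 12 months, small beside either effect above.

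**4. Effect on the visit-based test.** Inputs: paired difference 1.90, SD 0.9 and 12 evaluable participants (section VII, Sample size calculations). Assumptions: change is proportional to nights worn, and each participant's share of nights is uniform from 3/7 to 1, so the mean share is (3/7 + 1)/2 = 5/7. For a full-wear change D, the mean change is D × 5/7 and the SD is √(0.9² + D² × (4/7)²/12).

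- D = 1.90: mean 1.36, SD √(0.81 + 0.098) = 0.953. Simulated two-sided power at N = 12 is above 99%.
- D = 1.0 (assumed, smaller than planned): mean 0.71, SD √(0.81 + 0.027) = 0.915. Simulated power falls from about 94% with full wear to 69%.

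The SD rises by at most 0.953/0.9 − 1 = 6%. The loss in the second case therefore comes mainly from the smaller mean change, not from added spread between participants. At the planned difference, the test for a change between visits is barely affected.

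**The case against.** The strongest reply is that calendar age is a legitimate scale. The objective concerns spoilage under standard wear and care, and a replacement schedule is naturally stated in months. That stands: the visit-based test is not wrong, and cumulative nights need not replace it as the primary analysis.

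Second, a reader might infer that the lenses will in fact have very different numbers of nights. The documents do not show this. They give no adherence figure, they enrol people willing to follow the procedures, and they monitor compliance. Only the 6-month age difference between right and left lenses at the last visit is documented.

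Third, a reader might infer that pauses in wear after an adverse response will lengthen the apparent life of a lens. The Safety section describes discontinuing wear after a clinically significant response; it describes no pause followed by resumption. Nor does the plan estimate a replacement age from a curve, so it cannot be said that the resulting interval will be too long.

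Fourth, a supportive exposure analysis could sit in a statistical analysis plan that is not at hand. That is possible. But the protocol does name its time axis and tests, and a Friedman test takes no exposure term, so the addition would need its own analysis.

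Finally, adding nights worn as a covariate beside visit would be a poor remedy. Nights accumulate with visit and are zero for everyone at dispensing, so with 12 to 16 participants the two are hard to separate. Nights are also measured after baseline and may respond to discomfort. This stands, and the fix below avoids it.

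**Conclusion.** The point holds as a minor improvement. As written, the analysis pools lenses by nominal visit, no nights per week are fixed, and the journal has no analytic role. By design, the right lens graded at 12 months is about 6 months old while the left is about 12. Any further variation in wear is of unknown size; the contrast of 260 with 364 nights rests on an assumed 5 rather than 7 nights a week. The visit comparison remains valid as a primary test and, under the assumptions shown, keeps power above 99% at the planned difference of 1.90. What is weakened is the interpretation of a 12-month grade as a guide to replacement, unless the wear behind it is reported.

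**What to change.** Keep the visit-based analysis unchanged and add the following:

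- Derive from the journal the cumulative nights and hours on the specific lens being graded, starting the count again for the right lens when it is replaced at 6 months.
- Summarise these by visit and by eye beside the spoilage grades.
- Report one supportive analysis of spoilage against cumulative nights worn, with nights taking the place of visit rather than standing beside it, and allow for repeated grades and two eyes per participant. Present it as descriptive.
- Qualify any replacement interval by the wear observed.

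No new data are collected. The cost is entry of the journal and one extra analysis. The limits to state are that the journal is self-reported and that discomfort may reduce wear, so the relation between nights and spoilage should not be read as purely causal.

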4. Quantitative assessment of the lens surface protein deposition: The amount of protein and lipid deposited on the lens surface will be quantified using standardized lab procedures. This assessment will be performed on the right eye lens at the base line visit, 6-month visit and the left eye lens at the 12-month visit. At 6-month visit, a new lens with similar parameters will be dispensed for the right eye, as the original lens will be used for quantitative assessment.

IV. PARTICIPANT SELECTION

Number of participants

We are planning a study with an ordinal data response variable from matched pairs of study participants. We estimate that the difference in the lens spoilage grading between matched pairs is normally distributed with a standard deviation 0.9. To detect a true mean difference of 1.90 between pairs, we will need 12 subjects to achieve 80% power, assuming a Type I error rate of 0.05. To account for a 20% dropout rate, a total of 16 participants will be recruited. We will keep screening until we have met that target.

Inclusion Criteria

- Age between 18 to 40
- Have refractive error between -1.00 and -4.00D of Sphere, Astigmatism \leq 2.50D.
- Good eye health with no history of eye trauma or surgery, no eye disease
- Soft contact lens wearers willing to discontinue lens wear for at least 24 hours before participation. Individuals with or without a history of wearing rigid lenses (including orthokeratology) for a short-term (\leq 3months) and have discontinued wearing them for one month.
- Good general health and no medications which may influence eye health.
- Willing and able to comply with the research procedures and follow-up schedule.

Exclusion Criteria

- Age less than 18 years-old and more than 40 years-old
- Refractive error between less than -1.00D and more than -4.00D, astigmatism $>$ 2.50

Recruitment

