During the study, participants are required to wear OK lenses overnight and may experience possible temporary adherence of the contact lenses to the eye surface, mild irritation and discomfort due to lens edges rubbing against the eyelid margin, epithelial disruption or an allergic reaction to lens solution, mild discomfort, and a rare risk of corneal inflammation or infection.

Lens adherence is rare in open-eye rigid contact lens wear and is observed transiently on eye opening at a prevalence of about 80% after closed-eye rigid contact lens wear, where it may cause temporary localised corneal distortion and epithelial disruption. Previous research has demonstrated that these transient after-effects are rarely of clinical concern.

Epithelial disruption is a very common minor effect of wearing any contact lens, whether in research or clinical practice. The incidence of disruption varies considerably with wearing modality and lens type and is also patient-specific (for example, where there is underlying compromise of tear film or epithelial integrity prior to lens wear). Any such subjects will not be recruited for this research.

The risk of corneal inflammation and infection in short term soft and rigid contact lens wear are very low. Corneal infection is a rare disease in rigid contact lens wear and significantly lower than the risk posed by soft contact lens use. This slight risk is further reduced in this study because of the close clinical monitoring for warning signs and patient compliance, and the use of oxygen-permeable rigid lens materials appropriate for closed eye lens wear.

2. Likelihood and severity of complications:

The likelihood of developing corneal infections, including microbial keratitis, with orthokeratology (OK) lenses is relatively low, with an estimated incidence of 6.8 cases per 10,000 years of wear. This rate is lower than that associated with other overnight wear modalities of soft contact lenses. While the risk is rare, it cannot be classified as 'minimal' due to the potential for serious eye complications if an infection does occur. The severity of microbial keratitis can vary but may lead to significant discomfort, vision impairment, and, in severe cases, sight-threatening complications. This study aims to evaluate whether adjusting the lens replacement schedule can further mitigate this risk, enhancing the safety of OK lens wear for user.

3. Steps to minimise or prevent complications:

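### Soft lenses offered for driving to every follow-up visit conflict with their one-week reason and with the lens-free cessation period, and their use is not recorded

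*Protocol*

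**What the plan says.** In the Protocol, section III, Detailed Study procedure, the text on the baseline visit supplies daily disposable soft lenses "if participants are expected to drive to the research facility in all the follow-up visits". The reason comes in the same sentence: "Since it takes approximately one week for vision to be optimal with the study OK lens wear". The purpose follows: "These soft contact lenses will correct any expected residual power".

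The next item is headed "Follow-up visits (1-day overnight visit; 7-days visit; 14-days visit ;1month; 6 months; 9 months ;12 month; 2-weeks lens cessation visit", so the cessation visit counts as a follow-up visit. The text under that heading has participants stop lens wear for the two weeks after the 12-month visit, without saying whether this means OK lenses only or all lenses. It gives the purpose: "This cessation period allows for the evaluation of recovery and stabilization of eye surface parameters", with comparison to baseline.

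At entry, section IV, Inclusion Criteria, admits "Soft contact lens wearers willing to discontinue lens wear for at least 24 hours before participation". No comparable condition appears before any later assessment.

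Corneal and conjunctival staining and the two comfort questionnaires (OSDI, CLDEQ-8) are the secondary outcomes. Table 3 schedules the anterior eye check and the questionnaires at every visit from baseline to cessation. Its only wear record is the O-K Wear Time Journal.

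**The concern.** The study has one group, so what it says about the eye surface and comfort rests on change within each participant. A second contact lens, used only by some participants and introduced after baseline, enters that change directly. If it is worn shortly before staining is graded or a questionnaire is answered, part of the finding may belong to the soft lens.

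The cessation visit is where this matters most. Its purpose is to show whether the eye surface recovers once lens wear stops. Staining seen there in someone who had been wearing soft lenses could be reported as incomplete recovery from OK wear. If soft lens use was never recorded, no later analysis can separate the two.

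**Working it through.** The plan states no figure on this point, so there is nothing to reproduce. The check sets the provisions side by side.

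**1. Scope of supply against its reason.** The reason covers about one week.
- Table 3 has six visits after baseline: 1 day, 7 days, 21 days, 6 months, 12 months and cessation. Two fall within a week, leaving 6 − 2 = 4 outside it.
- The list in the follow-up heading differs and has eight entries. Two fall within a week, leaving 8 − 2 = 6 outside it.
- Both lists end with the cessation visit, so the conclusion is the same whichever applies.

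**2. Supply against the cessation period.** The instruction to stop lens wear can be read in two ways.
- *All lenses.* It then contradicts a soft lens provision that extends to all follow-up visits.
- *OK lenses only.* Soft lenses are then allowed on the way to the visit, and nothing bars them during the two weeks, so recovery is not assessed on a lens-free eye.

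Either reading needs a correction. The situation is plausible: participants enter with −1.00 to −4.00 D of myopia, a driver two weeks off OK lenses may need some correction, and the protocol mentions no other.

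**3. Control and recording.**
- The 24-hour condition applies to existing soft lens wearers at entry. No soft-lens-free interval is set before follow-up assessments.
- Nothing says when the soft lens is taken out on arrival.
- No row of Table 3 asks about soft lens wear. The journal logs lens use, bedtime and wake times, and its title and purpose concern overnight OK wear.

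**4. Possible length of exposure.** Visits take place in the morning, no more than two hours after waking. Soft lens wear that same morning is therefore under about 2 hours. At the cessation visit, under the OK-only reading, exposure could extend over the preceding two weeks.

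**5. What it can reach.**
- *Primary outcome:* grading of spoilage on the OK lens itself, so not directly affected.
- *Secondary outcomes:* staining and comfort, assessed at the 1-day, 7-day and cessation visits, where need for correction is most likely.
- *Tested time points:* section VII, Statistical Analysis, names baseline, 6 months and 12 months. None of those three visits is among them.

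**6. Size.** The shift in a group mean at a visit would be the proportion of participants with recent soft lens wear multiplied by the mean effect of that wear on the grade or score. The documents give neither quantity.

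**The case against.** The case against has real force. The supply depends on driving and on residual power, and the sentence opens with the one-week reason. The phrase about all follow-up visits can even be taken to describe who qualifies (people who will drive each time) rather than when the lenses are worn. The instruction to stop lens wear is not limited to OK lenses and may be meant to bar soft lenses too. On that view this is loose wording, not a demonstrated confounder.

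Several stronger readings are tempting, and the documents do not support them:

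- *That staining and comfort are measured with a soft lens in place.* No assessment is described that way. The soft lens is for the journey, and fit and on-eye spoilage assessments need the OK lens on the eye.
- *That baseline is soft-lens-free by rule.* The 24-hour condition governs entry. The baseline visit comes later, once the ordered lenses arrive, and nothing fixes soft lens status then.
- *That the 6- and 12-month comparisons are biased.* The wording permits soft lenses at those visits, but the stated reason gives no ground to expect residual power by then.
- *That a bias can be quoted.* If 25% to 75% of participants drove and recent wear added 0.5 Oxford grade, the shift would be 0.25 × 0.5 = 0.125 to 0.75 × 0.5 = 0.375 grade. Both inputs are assumptions without a source in the documents, so the range is not evidence.
- *That adverse events could not be attributed.* Section VI says "Corneal infection is a rare disease in rigid contact lens wear and significantly lower than the risk posed by soft contact lens use", but this compares the two lens types in general, and the same paragraph calls infection risk in short-term wear of either type very low. It supports recording soft lens wear, not the stronger claim.

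What survives the objection is that the supply has no stated end, that the text leaves the cessation period open to two incompatible readings, and that soft lens use goes unrecorded under either.

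**Conclusion.** The point holds in a narrow form. The soft lens provision is wider than its own reason and conflicts with the cessation period, and recent soft lens wear before staining and comfort assessments is neither controlled nor recorded. It concerns secondary outcomes and the recovery assessment, mainly at the 1-day, 7-day and cessation visits. Its numerical size cannot be derived from the documents.

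This rests on two assumptions: that at least some participants drive to visits, and that soft lens wear shortly before an assessment can influence staining or comfort. The documents quantify neither. It is a worthwhile, inexpensive improvement rather than a threat to the main result. It belongs in the protocol because an analysis plan cannot recover an exposure that was not collected.

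**What to change.** - **Wording.** Reconcile the soft lens provision with its one-week reason and with the cessation period, stating which lenses the cessation instruction covers. Which clinical rule applies is for the investigators to decide.
- **Recording.** Add one field to Table 3 at baseline and at every later visit, including cessation: whether a soft lens was worn in the last 24 hours, and the number of days of soft lens wear since the last visit. Including baseline matters because the entry condition does not settle soft lens status at that visit.
- **Analysis.** Keep all visits in the main analysis. Report staining and recovery without visits preceded by soft lens wear as a sensitivity analysis. Dropping such visits from the main analysis would selectively remove drivers from a study of 16.

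The cost is a wording change, one form field and a small additional analysis.
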